4.2. ELIGIBILITY

Adults and young people ≥ 12 years of age, and are classified as being part of one of the following patient groups:

1. A solid organ transplant recipient (n=12,000)
2. Patients with a rare autoimmune disease (n=12,000)
3. Patients with lymphoid malignancies (n=12,000)

The above patients will all be registered within the following national patient registries:

NHS BLOOD AND TRANSPLANT (NHSBT)

- I. The UK Transplant Registry held by NHSBT records all people in the UK with a functioning solid organ transplant. It already has successful linkage with Public Health England (PHE), National Immunisation Management Service (NIMS) and NHS Digital Tracing Service, providing data on vaccines, RT-qPCR COVID-19 infections and COVID-19 mortality data^{14,20}. Linkage for COVID-19 hospitalisations will be pursued for this project.
- II. Any adult or young person ≥ 12 years of age with a functioning transplant who has received 3 vaccines, will be eligible to participate.

THE NATIONAL DISEASE REGISTRATION SERVICE (NDRS)

NDRS, part of NHS Digital, comprises the National Congenital Anomaly and Rare Disease Registration Service (NCARDRS) and the National Cancer Registration and Analysis Service (NCRAS).

NCARDRS Rare disease register (NCARDRS)

- I. The REgistration of COmplex Rare Diseases – Exemplars in Rheumatology (RECODER) project within NCARDRS has already identified a cohort of 170,000 people with rare autoimmune diseases, many of whom are on immunosuppressants. Early results from this project has shown this group have a COVID-19-related mortality 2.4 times higher than people of the same age and sex in the general population. This cohort have validated disease diagnoses, and the registry can further identify those treated with Rituximab who are most at risk of lack of seroconversion following COVID-19 vaccination.
- II. The RECODER team already have access to National Immunisation Management Service (NIMS) data, RT-qPCR COVID-19 infection data, hospitalisation data (Hospital Episode Statistics) and Office for National Statistics mortality data for this cohort.
- III. Sampling will start with those people who have received treatment with Rituximab within the last 2 years, and a random sample of people with ANCA-associated vasculitis (n=9,854) or Lupus (n=41,261), or myositis or scleroderma or Giant Cell Arteritis ≥ 18 years of age who have received 3 vaccines will be eligible

National Cancer Registration and Analysis Service (NCRAS)

- I. The National Cancer Registration and Analysis Service (NCRAS) is responsible for cancer registration in England to support cancer epidemiology, public health, service monitoring and research.
- II. NCRAS actively records from health care data all patients with a diagnosis of cancer, and captures those patients receiving systemic anti-cancer therapy (SACT).
- III. People ≥ 18 years of age with a haematological malignancy who have received 3 vaccines will be eligible.

4.3. RECRUITMENT

To ensure study start time is aligned with vaccine roll out, recruitment of transplant participants (via NHSBT) will differ from cancer and autoimmune participants. This is a pragmatic decision based on differences in patient identifiable data recorded by the transplant and NDRS registries. The recruitment plans for the different cohorts are outlined below. Those wishing to participate in the study will register via a web portal developed by Ipsos MORI, as per REACT-2. They will consent electronically for participation in the study, subsequent data linkage on outcomes and willingness to be contacted about any future interventional research.

Participate information sheets will be available for all potential recruits, both paper and electronic access, depending on method of recruitment.

People with solid organ transplants: Transplant recipients will be invited to join the study by self-registration via the study web portal. Eligibility for transplant recipients will be assessed by them providing their NHS/CHI number and year of most recent transplant at the time of opting-in to the study. This will be immediately verified against the data held by the UK Transplant Registry before the patient proceeds to register for the study.

Participants will be invited to join ('opt-in' method) via communications via the British Transplant Society, NHSBT, transplant centres, patient charities and social media. Linkage to the NHSBT and NHS Digital registries will provide confirmation that the applicant is a solid organ transplant recipient and details of their vaccine status. Young transplant recipients (aged 12-15) will be additionally asked for their parent / guardian details upon registering on the study web portal.

Simultaneous application for access to NHS Digital will be made. If the target number of 12,000 participants is not reached via the opt-in methods by the time approvals are obtained, invitations will be sent out to a random sample of patients on the transplant registry akin to the patients on the NDRS databases below. Baseline participant characteristics of all participants on the transplant registry are available and will enable a description of the study participants in relation to the whole registry.

As of 14th February 2022, 2,500 adult solid organ transplant recipients have self-registered with the trial web portal and returned the results of the LFIA they received following their 3rd vaccine dose. Depending on availability of LFIA kits, participants who had an initial negative test will be further invited to perform an additional LFIA test, after receipt of their fourth or subsequent vaccine dose. These additional tests will provide data on the proportion of transplant recipients who seroconvert after their fourth or subsequent vaccine dose, despite being negative for anti-SARS-CoV-2 IgG antibodies after their third dose.

People with cancer and autoimmune disease: A random selection of eligible patients with autoimmune disease or haematological malignancy registered on the NCARDRS and NCRAS databases respectively, will be invited to join the study via personalised letter. Up to 2 reminders will be sent to potential participants. Patients responding to the invitation will register via the Ipsos MORI web portal. Using the experience from REACT-2, we estimate a response rate of 70% at registration and 85% at lateral flow test completion.

Following registration on the web portal and completion of a short online questionnaire including information on immunosuppression and medical history, sociodemographic variables and COVID-19-related behaviours and COVID-19 infection history, participants will be sent a LFIA test, which is provided with a detailed instruction booklet and link to an instruction video. For consenting young persons aged 12-15, the LFIA kit will be addressed to the parent / guardian whose name they have provided. Participants will be asked to carry out the test and follow the instructions to read the result and to take a photograph of the completed test, if possible. They will then provide their results via the web portal. A telephone helpline will be established to deal with any queries that may arise. Usability of the test has been assessed in REACT-2 study.

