1. INTRODUCTION

1.1. BACKGROUND

Immunocompromised individuals make up 500,000 of the UK population and comprise diverse population groups including those with autoimmune disease, solid organ transplants, and cancer. These individuals, especially those receiving concomitant immunosuppression, have a poor prognosis to infection with SARS-CoV-2. Whilst vaccination has conferred protection against severe infections for most individuals, the immunogenicity of SARS-CoV-2 vaccines have been shown to be suboptimal in immunocompromised individuals¹⁻⁴. Although immunogenicity does not necessarily correlate with clinical efficacy, the following data supports the continued risk of COVID-19 to immunocompromised individuals: 256 COVID-19-related deaths were reported by The Office of National Statistics in doubly vaccinated individuals from January to July 2021, 13.1% of whom were immunocompromised⁵; 40% of 152 doubly vaccinated hospitalised COVID-19 patients were immunocompromised as a result of chronic corticosteroid use, solid organ transplantation or anti-cancer therapy⁶; early data from NHS Blood and Transplant (NHSBT) suggests the mortality rates from SARS-CoV-2 infected vaccinated transplant patients is as high as 8%. With these emerging data, the Joint Committee of Vaccination and Immunisation (JCVI) approved 3rd vaccine doses for immunosuppressed people, in September 2021. Existing data on serological responses to 3rd and 4th dose vaccines in immunocompromised individuals is limited, but reports suggest that up to 25% of immunosuppressed individuals will remain unprotected even after 3 doses of vaccine^{7,8}.

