sociodemographic factors. Logistic regression models will be used to identify which of these factors are independently associated with developing antibodies following completion of the primary vaccine course.

6. The proportion of re-sampled transplant recipients (and 95% CI) with and without antibodies to SARS-CoV-2 following 4th dose who did not have antibodies after 3rd dose.

All outcomes will be adjusted for other known risk factors, and receipt of a subsequent 4th vaccine dose, as and where appropriate. Multiple imputation based on full conditional specification will be used to impute values of potential risk adjustment factors. The set of variables that will feature in the multiple imputation models will be described in the SAP. Sensitivity analyses will be conducted with cases with missing primary outcome data excluded.

A descriptive analysis aligned with above will additionally be performed for the young adult population.

Sample size

Each participant population will recruit 12,000 participants, and of these, we expect 85% to return their LFIA result (n=10,200). Following a third vaccine, we estimate approximately a third of participants in each group will have no SARS-CoV-2 antibodies, so this sample size will give a 95% confidence interval for the proportion of participants with no antibodies of $\pm 0.91\%$ for each participant group ^{7,8}. Even if the proportion of participants with no antibodies is 50%, the confidence interval would be $\pm 0.97\%$, so the large study size gives very good precision.

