The study has been powered to detect a difference of 2% in the proportion of participants free from RT-qPCR proven infection in the 6-month follow-up period, with 90% power and a 5% two-sided significance level. We have assumed a 2:1 ratio between those with and without SARS-CoV-2 antibodies, as described above. In the group with SARS-CoV-2 antibodies it has been estimated that 92.4% will be free from infection at 6 months and to detect a decrease to 90.4% in the group without SARS-CoV-2 antibodies using survival analysis methods, we require 9,273 participants in total in each participant population (justification for the expected rate is provided in Appendix 1 (Reproducibility statistical and design annex)). Our planned recruitment of 10,200 LFIA results per group therefore allows for up to a 9% withdrawal rate, which we think is very achievable as patients will have opted-in to the study initially. Higher LFIA return rates, a lower withdrawal rate, or combining data across the patient populations would enable smaller differences to be detected. We think that the timing of the study, and early evidence of strong engagement, would mean that only a relatively small number of patients would have received their 4th dose at the time of recruitment. With the emergence of Omicron, we expect infection event rates observed in the study to now be higher than those used in the original sample size calculation, even if the 4th dose reduce rates of RT-qPCR positive infection.

DIAGNOSTIC ACCURACY OF THE IMMUNOASSAYS

Using the threshold value for positivity on serological testing of ≥ 7.10 BAU/ml (n=183) on Abbott Architect Assay and confirmatory DABA results for available discordant samples (n=3) as the reference standard, the overall performance of the test in these combined cohorts produce an estimate of sensitivity of 92.0% (115/125; 95% CI 85.8% to 96.1%) and specificity of 95.1% (58/61; 95% CI 86.3% to 99.0%).

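### The transplant re-test result (item 6) measures LFIA conversion, not seroconversion: about 14% of first-test negatives would already have antibodies at the plan's own accuracy, and no minimum interval after the further dose is set

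*Combined protocol and SAP*

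**What the plan says.** Section 4.3 selects people for re-testing on a single self-read result: "participants who had an initial negative test will be further invited to perform an additional LFIA test", to be done "after receipt of their fourth or subsequent vaccine dose" and subject to kit supply. It describes the outcome as the proportion who seroconvert "despite being negative for anti-SARS-CoV-2 IgG antibodies after their third dose". Item 6 in section 7 carries this into the analysis as the proportion of re-tested transplant recipients "with and without antibodies to SARS-CoV-2 following 4th dose who did not have antibodies after 3rd dose".

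Section 7 also reports the accuracy of the LFIA against a laboratory reference standard (a threshold of 7.10 BAU/ml, with a confirmatory assay for three discordant samples): "sensitivity of 92.0% (115/125; 95% CI 85.8% to 96.1%) and specificity of 95.1% (58/61; 95% CI 86.3% to 99.0"%. Appendix 1 applies these figures to transplant patients. None of the six analysis items uses them.

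Objectives 1 and 2 say that antibodies are those detectable by LFIA testing. Item 6 and the re-test paragraph in section 4.3 do not carry that qualifier.

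On timing, item 1 requires the test to be at least 21 days after the 3rd dose and before a 4th. Items 2 and 6 state no minimum interval after the 4th or a later dose.

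**The concern.** Choosing people because one imperfect test was negative gathers that test's false negatives into the denominator. On re-testing, someone who already had antibodies after the 3rd dose may read positive and be counted as a new response, or may read negative again and be counted as a non-responder. The plan's wording does not allow for either. Item 6 is the only planned result on conversion among third-dose non-responders, so readers will want to take it as the yield of a further dose. As written, they could not separate new responses from first-test errors.

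The timing gap is a different problem with a different remedy. A test taken a few days after a 4th dose would count as a post-4th-dose result in items 2 and 6, whereas the same rule for the 3rd dose would exclude it.

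**Working it through.** **Inputs.** Sensitivity Se = 115/125 = 0.920 and specificity Sp = 58/61 = 0.951 (section 7, diagnostic accuracy). Exact binomial intervals give 85.8% to 96.1% and 86.3% to 99.0%, which reproduces the plan. The share without antibodies comes from the sample size text: "we estimate approximately a third of participants in each group will have no SARS-CoV-2 antibodies". The same text considers 50%. Section 1.1 gives "up to 25% of immunosuppressed individuals will remain unprotected even after 3 doses of vaccine"; that is a ceiling on the unprotected share, used here only as a low scenario.

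**Share of first-test negatives who already have antibodies.** With N the truly negative share:

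- First-test negative share: q = (1 − N)(1 − Se) + N × Sp
- Share of these with antibodies: f = (1 − N)(1 − Se) / q

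At N = 1/3: q = 2/3 × 0.080 + 1/3 × 0.951 = 0.0533 + 0.3169 = 0.370, and f = 0.0533/0.370 = **14.4%**.

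| Variation | f |
|---|---|
| N = 25% | 20.2% |
| N = 50% | 7.8% |
| N = 1/3, Se and Sp at lower limits (0.858, 0.863) | 24.8% |
| N = 1/3, Se and Sp at upper limits (0.961, 0.990) | 7.3% |
| One third is the LFIA-negative share | 17.0% |

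For the last row, N = (1/3 − 0.080)/(0.920 + 0.951 − 1) = 0.291, and f = 0.709 × 0.080/0.333 = 0.170. If N and the accuracy limits vary together, f runs from 3.8% to 33.0%.

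**Effect on the re-test proportion.** Let s be true conversion among those without antibodies, and r the degree to which a person's test behaviour repeats (0 = independent errors, 1 = full persistence). Then

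raw = f(1 − r)Se + (1 − f)[s × Se + (1 − s)(1 − r)(1 − Sp)].

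Take s = 0.42, the upper figure that section 1.1 cites for de novo responses after a 4th dose, purely as an illustration:

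| r | raw |
|---|---|
| 0 | 48.8% |
| 0.25 | 44.8% |
| 0.5 | 40.9% |
| 0.75 | 37.0% |
| 1 | 33.1% |

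At r = 1 with perfect second-test sensitivity the value is 0.856 × 0.42 = 36.0%. If the further dose made every first-test false negative read positive, it is 0.144 + 0.856 × (0.42 × 0.92 + 0.58 × 0.049) = 49.9%. The bias is zero near r = 0.43.

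**Against sampling error.** The number of re-tests is not stated. If all expected negatives among the 2,500 in section 4.3 were re-tested (an assumption), that is 2,500 × 0.370 = 926, and the half-width is 1.96 × √(0.42 × 0.58/926) = 3.2 points. The bias is inside that for r of about 0.23 to 0.64 and outside it at either end.

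**Timing.** Item 1 has a 21-day floor; items 2 and 6 have none. The documents give nothing from which to size the effect.

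**The case against.** The best reply is that this is mostly wording. The objectives define the quantity as detection by LFIA, section 4.3 names the LFIA as the instrument for both tests, and the accuracy is disclosed in the same section. Against an LFIA-defined quantity, a first-test negative is classified correctly. That stands, and it is why the raw proportion can stay. It does not rescue the terms used in item 6 and section 4.3, which speak of antibody status and seroconversion.

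A reader might infer that the re-test figure will overstate seroconversion, perhaps by about 14 points. The documents do not support that. Independent errors push the figure up, persistent errors push it down, and near half persistence they almost cancel; no repeatability data are given. With about 209 or fewer re-tests, the interval around a raw 48.8% would still reach 42%; around a raw 33.1% this holds with about 106 or fewer.

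A reader might also infer that test error is ignored altogether. Section 7 calls itself high-level and refers to a SAP; no separate detailed SAP was supplied, so a correction there cannot be excluded.

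On the inputs, the plan does not say whether one third is the true or the LFIA-negative share, so both results are shown. The 7% to 25% range sets both accuracy limits at their extremes together and is not a 95% interval.

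On timing, no item formally compares 3rd- and 4th-dose proportions, so no planned comparison is invalidated. What remains is that very early tests would be reported as post-dose results.

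**Conclusion.** The point holds as one of interpretation and labelling, with a modest analysis addition. By the plan's own accuracy figures, some 14% of the item 6 denominator would already have antibodies by the reference standard if one third are truly negative (17% if one third is the LFIA-negative share; 8% to 20% if 50% to 25% are truly negative; 7% to 25% at the joint accuracy limits). The raw result is therefore LFIA conversion at any degree of error persistence. The direction and size of its net bias for true seroconversion are not established.

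The missing minimum interval in items 2 and 6 is plain from the text, with unknown effect.

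Severity is minor: item 6 is descriptive and lies outside the four objectives. The conclusion assumes that the quoted accuracy carries over to self-testing in this cohort.

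**What to change.** **1. Label and test-error range.** In item 6 and section 4.3, describe the group as those who tested LFIA-negative after the 3rd dose and the result as LFIA conversion. Keep the raw proportion and its confidence interval as the reported result. Add one prespecified sensitivity range:

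- Take q only from adult transplant first LFIAs done at least 21 days after the 3rd dose and before any 4th. The protocol also admits people who have already had a 4th dose, and their first tests would distort q.
- Draw Se and Sp from 115/125 and 58/61. Compute N = (q − 1 + Se)/(Se + Sp − 1) and f = (1 − N)(1 − Se)/q.
- Compute s = [raw − a f − (1 − f) b] / [(1 − f)(Se2 − b)]. Here a, the share of first-test false negatives that read positive on re-test, runs from 0 to 1. The false-positive share b runs from 0 to 1 − Sp. Se2, the second-test sensitivity in new responders, is set below, at and above 92%. Values below matter because section 1.1 says antibody concentrations stay generally low in this population.
- Truncate to 0–1, say when this occurs, and report the result as a bound, not as a corrected estimate.

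The range may be wide. At the point values above with Se2 = 0.92, a raw 42% maps to (0.42 − 0.144 − 0.856 × 0.049)/(0.856 × 0.871) = 31% at a = 1, b = 0.049, and to 0.42/(0.856 × 0.92) = 53% at a = b = 0.

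**2. Timing.** In items 2 and 6, include only LFIA tests taken at least 21 days after the most recent vaccine dose, using the linked vaccine dates, and report how many tests this excludes.

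**Cost.** Wording changes and a short calculation, with no extra kits or data collection. Some early tests are lost and the reported range is wide.

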4.4. WITHDRAWAL CRITERIA

All participants are free to withdraw at any time without giving reasons and without prejudice. Data provided after registration will remain in the web portal as they cannot be deleted. Participants who have received a test kit but wish to withdraw can simply discard the test kit.

5. ADVERSE EVENTS

5.1. DEFINITIONS

Adverse Event (AE): any untoward medical occurrence in a patient or clinical study subject.

Serious Adverse Event (SAE): any untoward medical occurrence or effect that:

- **Results in death**
- **Is life-threatening** – *refers to an event in which the subject was at risk of death at the time of the event; it does not refer to an event which hypothetically might have caused death if it were more severe*
- **Requires hospitalisation, or prolongation of existing inpatients' hospitalisation**
- **Results in persistent or significant disability or incapacity**
- **Is a congenital anomaly or birth defect**

Medical judgement should be exercised in deciding whether an AE is serious in other situations. Important AEs that are not immediately life-threatening or do not result in death or hospitalisation but may jeopardise the subject or may require intervention to prevent one of the other outcomes listed in the definition above, should also be considered serious.

5.2. REPORTING PROCEDURES

All adverse events should be reported. Depending on the nature of the event the reporting procedures below should be followed. Any questions concerning adverse event reporting should be directed to the Chief Investigator in the first instance.

5.3.1 Non serious AEs

All such events, whether expected or not, should be recorded- it should be specified if only some non-serious AEs will be recorded, any reporting should be consistent with the purpose of the trial end points.

5.3.2 Serious AEs

An SAE form should be completed and emailed to the Chief Investigator within 24 hours. However, infections and death due COVID-19, and hospitalisations for elective treatment of a pre-existing condition do not need reporting as SAEs.

All SAEs should be reported to the London-Central REC where in the opinion of the Chief Investigator, the event was:

- ‘related’, ie resulted from the administration of any of the research procedures; and
- ‘unexpected’, ie an event that is not listed in the protocol as an expected occurrence

Reports of related and unexpected SAEs should be submitted within 15 days of the Chief Investigator becoming aware of the event, using the NRES SAE form for non-IMP studies. The Chief Investigator must also notify the Sponsor of all related and unexpected SAEs.

Contact details for reporting SAEs
[contact]

CI email (and contact details below)
[contact]

